The primary goal of Aim 2 is to test the incremental efficacy of the AR app when added to standard tobacco quitline services. We will recruit and randomize participants to one of two treatment arms: (1) quitline only (QLO) or (2) quitline plus the AR app (QL+AR). In the interest of rapid dissemination and implementation pending positive findings, we have designed procedures with future scalability in mind. Participants will be recruited via the Tobacco Free Florida Quitline and referred to the study team via quitline enrollment agents. Participants who return a baseline questionnaire will be directed to download the app on their personal device and will complete the study. The primary outcome will be biochemically-confirmed tobacco abstinence assessed at around 6 months in a subset of participants.

Participants and Recruitment (see 3.2 above)

Randomization

Block randomization (block sizes=8) will be used to assign 2072 enrolled participants to one of the two conditions. The randomization order will be generated by [name] and implemented within REDCap.

Quitline Services

All study procedures have been developed in close coordination with Tobacco Free Florida, the Florida Department of Health, and RVO Health, the quitline contractor will oversee all aspects of the quitline, including supervising staff to coordinate project activities, modification of quitline software to support the screening and referral of callers, and management of data collection by quitline staff.

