Follow-up questionnaires will be sent to all participants via REDCap around 5 weeks and 6 months after-baseline completion. A subset of participants (40%, approximately 100) who self-report cigarette smoking abstinence at around 6 months will be mailed a saliva collection kit for cotinine-based biochemical confirmation of abstinence. A subset of participants (n=40) from QL+AR will complete a phone interview at the end of treatment, as will a subset of quitline supervisors (n=10) and all App coaches.

Compensation and Retention

For completion of measures at baseline, and around 5 weeks and 6 months after baseline survey completion, participants will receive a \$20 gift card (up to \$60 total). For each week they complete at least 70% of the daily diary questions (5 days), they will receive a \$10 gift card (up to \$50 total). Thus, most participants will be compensated up to \$110. Participants who complete the interview, will be compensated \$20. Participants who return a saliva sample will be compensated \$25.

To aid in retention, the following procedures will take place: collection of full contact information; text reminders and phone calls to follow-up on incomplete surveys; and collection of names and contact information of at least 2 collaterals (i.e., relatives, friends) who can help us reach lost participants.

Treatment Delivery and Fidelity for AR and Quitline Coaching

Although we expect minimal use of App coaches based on the comprehensive app content, we will monitor and assess coaching fidelity. App coaches will be part of the study team. With an eye toward scalability, qualifications will mimic those of quitline coaches (e.g., Bachelor's degree, tobacco abstinent). Training will be manualized and conducted by Drs. [name] and [name], given their experience with exposure-based treatments. Training (8-10 hours) will be a combination of reading, didactics, and role playing. We will develop a measure to assess adherence and competence to be used during the training period. Weekly supervision will occur to ensure App coaching is delivered consistently. Coaches falling below performance

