Data Management. Baseline, 5-week, and 6-month survey data will be exported from REDCap as .CSV files, which will be read into SAS version 9.4 (SAS Institute, Cary, NC) on a weekly basis during data collection. Data review and primary data analyses will be performed using SAS version 9.4. [name] will oversee the data management, provide the PIs with reports and summaries on a regular basis, and perform the final analyses.

Sample Size and Study Power Analysis. The primary statistical analysis for Aim 2 will use logistic regression to compare abstinence rates at the 6-month assessment between QL+AR and QLO conditions. Preliminary analyses will be used to identify demographics and tobacco history variables that predict either missing surveys or abstinence around 5 weeks and 6 months. These variables will be used in a multiple imputation model to manage missing data. Based on abstinence rates from quitline/telephone counseling (Fiore et al., 2008; Matkin et al., 2019; Pinero et al., 2020), the estimated 7-day point prevalence abstinence rate around 6 months for the QLO condition is 10%. With 1036 randomized to each condition, power was calculated for the 725 participants expected to achieve 48-hours of abstinence in each condition (to activate the AR app). Power $\geq .80$ to detect an abstinence rate of at least 15% (OR = 1.59) in the QL+AR condition using alpha = .05, a 2-sided test, and allowing 5% of variance in abstinence rates to be accounted for by other variables. A comparable analysis using all 2072 randomized participants (the 1450 who do achieve 48-hours of abstinence plus the 622 who do not) will have lower expected abstinence rates. Estimating that 7% of all QLO participants will be abstinent, power $> .80$ to detect an abstinence rate of at least 10.6% for QL+AR (OR = 1.57) using alpha = .05, a 2-sided test, and allowing 5% of variance in abstinence rates to be accounted for by other variables.

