Data Analysis Overview. Descriptive statistics will be used to review all variables in the study prior to hypothesis testing. Data transformations will be made as needed. Treatment group differences in baseline measures will be assessed and any variable with a group difference of $p < .10$ will be incorporated into analyses focusing on intervention effects. All analyses described below will be performed for those who achieved 48 hours of self-reported abstinence (n=1450) as well as the full sample of those enrolled (N=3590). The former is relevant to assessing the efficacy of the app specifically, whereas the latter will reflect the overall incremental effectiveness of the app from the perspective of the quitline. Full-sample versus AR-sample differences in baseline measures will be evaluated.

To manage missing data, multiple imputation under the Missing at Random assumption will be applied using a Markov Chain Monte Carlo method (Schafer, 1997) via PROC MI in SAS, given the expected nonmonotonic missing data patterns and the expected large number of auxiliary variables (e.g., baseline measures that predict smoking status at follow-up) to be determined by preliminary analyses. The imputation model will

include smoking status around 5 weeks, which is expected to be a primary predictor of smoking status around 6 months.

In addition, any other measures acquired around 5 weeks that are unique predictors of missingness or smoking status around 6 months will be included in the imputation model. Finally, a post hoc approach (Rubin, 1987) will address the possible influence of Missing Not at Random. As done in recent studies (e.g., [name] et al., 2016; Martinez et al., in press), the post hoc adjustment will be small-to-medium in size (akin to Cohen's $d=0.35$) in accordance with missing implies smoking. Twenty data sets will be generated. Therefore, all analyses of the primary outcome will be performed on complete data sets (i.e., intent-to-treat) following multiple imputation.

Analytic Plan for Addressing Specific Aims.

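### The stated power of at least .80 assumes every 6-month outcome is observed, and the full-sample size is given as both 3590 and 2072

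*Combined protocol and SAP*

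**What the plan says.** Section 5, Sample Size and Study Power Analysis, sets out the primary calculation: "With 1036 randomized to each condition, power was calculated for the 725 participants expected to achieve 48-hours of abstinence in each condition". The inputs are 10% abstinence in QLO against 15% in QL+AR (OR 1.59), two-sided alpha .05, and 5% of outcome variance attributed to other variables. The result is power of at least .80. A second calculation uses everyone randomized, at 7% against 10.6% (OR 1.57), and gives power above .80.

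The plan also expects incomplete follow-up:

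- Section 4.3, Compensation and Retention, collects contacts "who can help us reach lost participants".
- The power section itself plans to look for variables that "predict either missing surveys or abstinence around 5 weeks and 6 months".
- The Data Analysis Overview chooses its imputation method "given the expected nonmonotonic missing data patterns". The imputation model includes "smoking status around 5 weeks, which is expected to be a primary predictor of smoking status around 6 months".

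On the size of the full sample, the Data Analysis Overview says analyses will be run in the 48-hour abstainers (n=1450) "as well as the full sample of those enrolled (N=3590". The power section says: "A comparable analysis using all 2072 randomized participants (the 1450 who do achieve 48-hours of abstinence plus the 622 who do not". Section 4.3, Randomization, says block randomization "will be used to assign 2072 enrolled participants to one of the two conditions".

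**The concern.** Section 4.2 (App Use, Assess) gives the 70% behind the 725. It is the share expected to qualify for the AR sessions, not the share expected to return a 6-month outcome. A reader who sees 1036 reduced to 725 could easily take it for a dropout allowance.

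The figure of .80 will be read as the power of the analysis the trial will actually run. If it refers to a data set with no missing outcomes, the chance of detecting the target effect is overstated for both the primary and the full-sample comparison, and a null result would look more informative than it is.

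The second point is simpler. The full-sample analysis set has two sizes within Section 5, and the odd one stands in the paragraph that defines the sets for all the analyses that follow.

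**Working it through.** **Formula.** Pooled two-proportion z test, two-sided alpha .05, with p̄ the mean of the two rates:

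power = Φ( [ |p2 − p1|·√n − 1.96·√(2·p̄(1 − p̄)) ] / √(p1(1 − p1) + p2(1 − p2)) )

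Here n is the effective number per arm: the planned number × 0.95 for the 5% variance allowance.

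**Step 1: reproduce the plan's figures, complete data.**

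- Primary set: 1036 × 0.70 = 725; n = 725 × 0.95 = 688.75. Power = Φ((1.312 − 0.917)/0.466) = **0.802**. OR = (.15/.85)/(.10/.90) = 1.588, as stated.
- Full sample: n = 1036 × 0.95 = 984.2. Power = Φ((1.129 − 0.785)/0.400) = **0.805**. OR = (.106/.894)/(.07/.93) = 1.575, as stated.

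Both figures reproduce using all 725 and all 1036 per arm, so no missing-data allowance is built into them. On this formula, power drops below .80 once about 0.5% (primary) or 1.3% (full sample) of the outcome information is lost. A Wald calculation on the log-odds scale gives 0.796 and 0.800 even with complete data, so the exact crossing point depends on the formula.

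**Step 2: allow for missing outcomes.** Let r be 6-month retention and f the share of the missing information that imputation recovers, mainly through 5-week smoking status. Then n = planned n × 0.95 × [r + (1 − r)·f]. The documents give neither r nor f; the values below are assumptions. Example: primary set, r = 0.8, f = 0.5 gives n = 688.75 × 0.90 = 619.9 and power 0.759.

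| Retention | Primary, f = 0 | f = .25 | f = .5 | Full, f = 0 | f = .25 | f = .5 |
|---|---|---|---|---|---|---|
| 100% | 0.802 | 0.802 | 0.802 | 0.805 | 0.805 | 0.805 |
| 90% | 0.759 | 0.771 | 0.781 | 0.763 | 0.774 | 0.785 |
| 80% | 0.709 | 0.735 | 0.759 | 0.713 | 0.739 | 0.763 |
| 70% | 0.651 | 0.695 | 0.735 | 0.655 | 0.699 | 0.739 |

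The f = 0 columns are the complete-case lower bound.

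**Step 3: detectable rate at 80% retention.** Holding power at .80, the detectable QL+AR rate in the primary set is 15.6% with nothing recovered and 15.3% with half recovered, against the stated 15%. In the full sample it is 11.0% and 10.8%, against 10.6%.

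**Step 4: without the 5% variance allowance.** Complete-data power is 0.822 (primary) and 0.825 (full). In the primary set, 90% retention gives 0.780 to 0.802 and 80% retention gives 0.731 to 0.780, as f goes from 0 to .5.

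**Step 5: the two sample sizes.** 1450 + 622 = 2072, and 1450/2072 = 70.0%, which agrees with Section 4.2. Against 3590, the non-achievers would be 3590 − 1450 = 2140, not 622, and the achievers 1450/3590 = 40.4%. The figure 2072 appears in Sections 1, 3.2, 4.3 and 6 and three times over in Section 5 (the Aim 2 overview, the power analysis and Aim 2a). If 3590 were real (1795 per arm), full-sample power with complete data would be 0.960 rather than 0.805.

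**The case against.** - **A retention figure may exist out of view.** Figure 5 (participant flow) is not shown, and Section 5 refers to a separate Statistical Design and Power attachment. Retention could be stated in either. This stands as a caveat on whether retention is stated anywhere. It does not alter the finding that the quoted power uses all 725 and all 1036.
- **The analysis runs on completed data sets.** Imputation makes 725 per arm the size of the analysis set, so the calculation is arithmetically right. But imputation fills rows without restoring the information of observed outcomes; the between-imputation variance enters the standard error. The table gives credit for up to half the loss.
- **The plan has slack elsewhere.** Section 4.2 says at least 70% should qualify. If 80% did (an assumption), 829 per arm would enter the primary set, and power would be 0.81 at 90% retention with nothing recovered, or at 80% with half recovered. This is fair, but the plan does not quantify it. The 5% allowance is assigned to covariates. Removing it just holds .80 at 90% retention with half recovered, and not at 80%.
- **More abstainers may be expected.** Section 4.3 puts 40% of self-reported abstainers at about 100, so about 250 in all. The full-sample power rates imply 1036 × (.07 + .106) = 182. More events at the same OR would raise power. The two counts are not reconciled, and cotinine testing may disconfirm some of the 250.
- **The 10% may already count non-responders as smokers.** The documents do not say so, and the planned primary analysis is imputation under Missing at Random. If 10% and 15% are instead rates among responders and missing were counted as smoking, power in the primary set would be .753, .697 and .633 at 10%, 20% and 30% missing.
- **The practical shift is modest.** At 80% retention the detectable rate moves by 0.3 to 0.6 percentage points in the primary set. That is true, and it is why only a restatement is asked for.

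**Conclusion.** The concern holds on both counts. The power of at least .80 is correct arithmetic for complete 6-month outcomes, which the plan itself does not expect, and it leaves almost no reserve. Under assumed retention of 70% to 90% and recovery by imputation of none to half of the lost information, power is about 0.65 to 0.78 in the primary set and 0.66 to 0.79 in the full sample. The size depends on those assumptions, on 70% qualifying, and on the 5% variance allowance being used for covariates. The absence of any missing-outcome term in the quoted figures does not depend on them.

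The 3590 conflicts with 2072 everywhere else and with the plan's own split of 1450 and 622. It looks like a leftover number, and it has no bearing on primary power.

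**What to change.** 1. In Section 5 (the Aim 2 overview and the Sample Size and Study Power Analysis), state the expected 6-month retention. Restate power and the detectable QL+AR rate at that value for both the n=1450 and the full-sample analysis. A short table over 70% to 90% retention would do, giving the share of missing information that 5-week status is assumed to recover. Say also whether the 10% and 7% QLO rates already count non-responders as smokers.
2. In the Data Analysis Overview, replace 3590 with the actual full-sample number, which is 2072 everywhere else. If 3590 is the current figure, update the other sections, the 622 and the full-sample power instead.

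The cost is text only. The stated power becomes less favourable or the detectable difference slightly larger; enrolment and the analysis stay as planned.

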Aim 2a. The primary test of the efficacy of QL+AR over QLO will use logistic regression on biochemically-confirmed abstinence around 6 months after baseline survey completion. This will be performed on the 20 imputed data sets using those participants who exhibited 48 hours of abstinence (n=1450). The model will include demographics and smoking-related variables that were found to uniquely predict self-reported abstinence at 6 months based on preliminary analyses. A parallel analysis will be performed to evaluate efficacy for all enrolled (N=2072; i.e., beyond those who exhibit the required 48-hour abstinence to engage the AR intervention). A second test of effectiveness will use generalized estimating equations (GEE) with both the 5-week and 6-month abstinence as the outcomes. This approach permits evaluation of a change in abstinence from around 5 weeks to 6 months and an assessment of the intervention at around 5 weeks in the context of the primary outcome (using a timespecific contrast).

Aim 2b. Prospective moderators of the QL+AR intervention will be explored, separately, by extending the analyses described above through the inclusion of the moderator and the moderator x intervention as predictors of the dependent measure. A significant interaction term supports the variable as a moderator, which will be explored by assessing condition differences for each level of categorical moderators and for levels of continuous moderators created via median splits, tertiles, or quartiles. The following baseline measures will be evaluated: sex, nicotine dependence, trait cue reactivity, smoking status during treatment, quitline use, and NRT use.

Prospective predictors of the AR intervention will be evaluated using only participants from the QL+AR arm. Similar to the analyses described above, AR-related variables will be added to a logistic regression model of abstinence at around 6 months that includes demographics and baseline smoking-related variables found to be predictors of abstinence among QL+AR participants. The following variables will be explored: initial cue reactivity, extinction magnitude and latency, indices of treatment engagement, and App coach use.

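### Multivariate-normal MCMC imputation of a 7-15% binary abstinence outcome, with no stated 0/1 conversion or role for treatment arm, biases the primary odds ratio in a direction the plan leaves open

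*Combined protocol and SAP*

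**What the plan says.** Section 5 states twice, in the Aim 2 overview and in Data Analysis Overview, that "multiple imputation under the Missing at Random assumption will be applied using a Markov Chain Monte Carlo method". Data Analysis Overview names the imputation tool as a "Markov Chain Monte Carlo method (Schafer, 1997) via PROC MI in SAS", chosen "given the expected nonmonotonic missing data patterns and the expected large number of auxiliary variables". It adds "Twenty data sets will be generated". The imputation model will "include smoking status around 5 weeks", which is also a smoked-or-not variable. A missing-not-at-random step follows: "the post hoc adjustment will be small-to-medium in size (akin to Cohen's $d=0.35$) in accordance with missing implies smoking".

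Under Aim 2a in the Analytic Plan, the primary test "will use logistic regression on biochemically-confirmed abstinence around 6 months after baseline survey completion", and "This will be performed on the 20 imputed data sets". Section 4.4 (Tobacco Abstinence) defines the outcome as 7-day point prevalence abstinence, a yes/no variable. The power paragraph plans for 10% against 15% in those who reach 48 hours of abstinence (725 per arm), and 7% against 10.6% in all randomised (1036 per arm).

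Nowhere does the combined document give a rule for turning imputed values into 0 or 1, say whether arm is in the imputation model or imputation is done by arm, or state an expected missing fraction.

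**The concern.** PROC MI's MCMC option treats all imputed variables as jointly normal. This is a property of the named method; the plan does not use those words. For a 0/1 variable with a mean near 0.10, the draws are continuous and often negative. Logistic regression cannot use them until they are converted.

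Conversion is not neutral at low event rates. The share of normal draws above a cut-off is a different function of the true rate from the rate itself, so a difference between arms is compressed or stretched. Which of these happens depends on whether the arms share a variance (one joint model) or have their own (imputation by arm). The plan fixes neither. These data sets feed the primary test, the full-sample test and, through the 6-month endpoint, the cost per quitter in Aim 3a.

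**Working it through.** **The plan's own power figure.** Inputs from the Sample Size and Study Power Analysis paragraph: 725 per arm, 10% and 15%, two-sided alpha .05, 5% of variance explained by covariates. Effective n = 725 × 0.95 = 688.75.
- Null SE = √(2 × 0.125 × 0.875 / 688.75) = 0.01782
- Alternative SE = √((0.09 + 0.1275) / 688.75) = 0.01777
- Power = Φ((0.05 − 1.96 × 0.01782) / 0.01777) = Φ(0.848) = 0.80

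Full sample: 1036 × 0.95 = 984.2 gives 0.805. Both stated figures are reproduced. They assume no missing outcomes.

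**Closed-form check, no auxiliary variables.** The imputed rate is P(draw > 0.5) = 1 − Φ((0.5 − p)/SD).
- Joint model, common SD = √((0.09 + 0.1275)/2) = 0.330. 10% becomes 1 − Φ(1.213) = 11.3%; 15% becomes 1 − Φ(1.061) = 14.4%. The 5-point gap shrinks to 3.1 and the odds ratio among imputed values is 1.33.
- Joint model, full sample: 7% and 10.6% become 6.4% and 8.2%, odds ratio 1.30.
- By arm, SD 0.300 and 0.357: 10% becomes 9.1% and 15% becomes 16.3%. The gap grows to 7.2 and the odds ratio is 1.95.

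The same rounding rule therefore compresses or stretches the effect according to how arm is handled. Stretching also magnifies chance differences, which is how type I error rises.

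**Simulation of the whole analysis.** 1500 trials per setting, 20 imputations, Rubin's rules, unadjusted log odds ratio. Assumed, because the documents give no values: 6-month outcome 20% or 40% missing at random in a non-monotone pattern, 5-week outcome also partly missing, 5-week abstinence 25% and 32%, 5-week predictor weak (log odds ratio 0.5) or strong (2.5). Ranges span the weak and strong predictor. Each cell gives the abstinence rates (QLO/QL+AR), the odds ratio, and the rejection rate.

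| Set (truth), missing | Logistic imputation | Normal, joint, rounded at 0.5 | Normal, by arm, rounded at 0.5 |
|---|---|---|---|
| Primary (10%/15%), 20% | 10.0/15.0; 1.60; .73-.75 | 10.3/14.9-15.0; 1.54-1.55; .68-.71 | 9.9/15.3-15.4; 1.66-1.67; .79 |
| Primary, 40% | 10.0/15.0-15.1; 1.59-1.61; .60-.63 | 10.6/15.0; 1.49-1.50; .50-.54 | 9.8/15.7-15.8; 1.73-1.74; .72-.74 |
| Full (7%/10.6%), 20% | 7.0/10.6; 1.57-1.58; .73-.74 | 6.9-7.0/10.2; 1.53; .69 | 6.6/10.5-10.6; 1.67-1.68; .80-.81 |
| Full, 40% | 7.0-7.1/10.6-10.7; 1.58; .60-.61 | 6.9-7.0/9.9; 1.47-1.48; .52 | 6.3/10.6-10.7; 1.79; .75-.78 |

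The Monte Carlo standard error of a rejection rate near .70 is √(0.7 × 0.3/1500) = 0.012.

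**Type I error at 10% in both arms:** logistic .03-.04; joint with rounding .015-.032; by arm .06-.07 at 20% missing and .10-.11 at 40%. Further runs put the by-arm figure at about .12 with 35% missing and the by-arm odds ratio at 1.64-1.77. The higher by-arm rejection rates in the table are therefore not usable power.

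**Other conversions, joint model.** Adaptive rounding gives odds ratios of 1.46-1.55. Clipping the draw to 0-1 and using it as a Bernoulli probability gives 1.35-1.49.

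**Standard errors.** In separate runs (600 trials, 36% missing, strong predictor, 5-week smokers three times as likely to be missing at 6 months), joint imputation with rounding had a mean Rubin standard error of 0.181 against an empirical SD of 0.162. Logistic imputation gave 0.183 against 0.182.

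**The case against.** Three stronger readings are tempting, and the documents support none of them.

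- **Rounding inflates abstinence in both arms.** Under 0.5 rounding in a joint model, the table shows only the primary-set control arm rising, by 0.3-0.6 points, while the full-sample QL+AR rate falls. Both arms do rise when 5-week smokers drop out more (11.4%/16.1% against a truth of 10%/15% at 36% missing) or under the Bernoulli conversion. The plan fixes neither the dropout pattern nor the conversion.
- **The planned analysis can only be conservative.** This holds only if arm is a predictor in one joint model. Imputation by arm is not excluded, and it reverses the bias.
- **The method explains why power would fall below .80.** Logistic imputation also gives only .60-.75. Most of the loss is missing data, which the power calculation ignores; the method accounts for the 4-10 point gap.

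Other objections carry weight. The conversion rule is unstated rather than known to be wrong, and Section 5 points to a Statistical Design and Power attachment that may say more. The d = 0.35 shift also matters, because the text does not make clear whether the 20 analysed data sets are the shifted ones. With a 0.35 SD shift on the normal scale and data truly missing at random, a joint model with rounding gave 9.3%/13.8% (odds ratio 1.57) at 23% missing and 9.0%/13.1% (1.54) at 35%, below the true rates. Finally, many auxiliary variables were a stated reason for MCMC, and logistic imputation of a rare outcome is most fragile there. That qualifies the fix but does not rescue rounding.

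**Conclusion.** The point holds as one of unsuitable method and incomplete specification. A normal-theory imputation of a low-rate binary outcome feeds a logistic regression, and choices absent from the document decide whether the odds ratio is biased down with lost power, or up with type I error about double the nominal level. In the joint-model runs the odds ratio falls by about 0.05-0.11. Arm-level rates under 0.5 rounding move by about a point either way (at most 1.4 in these runs), depending on who drops out.

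The directions follow from the closed form. The sizes rest on assumed missing fractions of 20-40%, assumed 5-week rates and an assumed predictor strength, and would be small if few outcomes are missing. The main simulation leaves out the d = 0.35 shift. This should be changed before analysis, but it does not undermine the design.

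**What to change.** In both places in Section 5 where MCMC is named (the Aim 2 overview and Data Analysis Overview), specify instead:

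1. Fully conditional specification in PROC MI, with logistic models for 5-week and 6-month abstinence and other binary variables, and regression or predictive mean matching for continuous ones. This handles the non-monotone pattern and produces 0/1 values directly.
2. Treatment arm as a predictor in every imputation model.
3. Twenty imputations, as now.
4. The primary analysis on the missing-at-random data sets, with the d = 0.35 shift as a named sensitivity analysis on the log-odds scale. One standard conversion is 0.35 × π/√3 = 0.63, which multiplies the odds of abstinence among the missing by exp(−0.63) = 0.53.
5. A check of the logistic models for separation, with a rule for trimming the auxiliary list if it occurs.

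If MCMC is kept, the plan should state the conversion rule and the handling of arm, and show type I error for that combination by simulation.

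The cost is SAP wording and a few lines of SAS code. The one real downside is item 5: with a 7-15% outcome, some of the many planned auxiliaries may have to be dropped.
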